--	--

	
 
• Ventricular arrhythmias.
 
• Supraventricular and nodal arrhythmias not controlled with medication.
 
• Other cardiac arrhythmia not controlled with medication.
 
• Participants with corrected QT (QTc) <math>\geq 470</math> ms using Fridericia correction (QTcF) on the screening electrocardiogram (ECG) (using the average QTcF of the triplicate ECGs).
 
 
 
• Presence or history of interstitial lung disease or interstitial pneumonitis, including clinically significant radiation pneumonitis (i.e., affecting activities of daily living or requiring therapeutic intervention).
 
• Participants have received anti-cancer therapies within the following time frames prior to the first dose of study treatment:             
 
• Conventional cytotoxic chemotherapy: <math>\leq 4</math> weeks (<math>\leq 6</math> weeks for nitrosoureas and mitomycin-C).
 
• Biologic therapy (e.g., antibodies): <math>\leq 4</math> weeks.
 
• Non-cytotoxic small molecule therapeutics: <math>\leq 5</math> half-lives (if half-life known) or <math>\leq 2</math> weeks
 
• Other investigational agents: <math>\leq 4</math> weeks.
 
• For Phase II Group 5: Previous anti-cancer and investigational agents within 4 weeks or <math>\leq 5</math> x half-life of the agent (whichever is shorter) before first dose of capmatinib. If previous treatment is a monoclonal antibody, then the treatment must be discontinued at least 4 weeks before first dose of capmatinib. If previous treatment is an oral targeted agent, then the treatment must be discontinued at least 5 x half-life of the agent.
 
• For Phase II Group 5: Treatment with a prior first or second generation EGFR TKIs (e.g., erlotinib, gefitinib, afatinib, dacomitinib), osimertinib or another third generation EGFR TKIs within 14 days or approximately 5x half-life, whichever is shorter, of the first dose of study treatment (if sufficient washout time has not occurred due to schedule or PK properties, an alternative appropriate washout time based on known duration and time to reversibility of drug related adverse events could be agreed upon by Novartis and the Investigator).
 
 
 
• Radiation therapy (palliative setting is allowed.): <math>\leq 4</math> weeks, for asymptomatic brain metastases <math>\leq 2</math> weeks.
 
• Major surgery: <math>\leq 2</math> weeks  For Phase II Group 5: Major surgery (e.g., intra-thoracic, intra-abdominal or intra-pelvic) within 4 weeks prior (2 weeks for resection of brain metastases) to starting capmatinib or who have not recovered from side effects of such procedure. Video-assisted thoracic surgery (VATS) and mediastinoscopy will not be counted as major surgery and participants can be enrolled in the study <math>\geq 1</math> week after the procedure.
 
• Participants that have not recovered from all toxicities related to prior anticancer therapies to grade <math>\leq 1</math> (CTCAE version 5.0). (Participants with any grade of alopecia are allowed to enter the study).
 
• Participants in Phase Ib and Phase II Groups 1 to 4 have out of range laboratory values defined as:             
 
• Absolute Neutrophil Count (ANC) <math>< 1.5 \times 10^9/L</math> (<math>1.5 \times 10^3/\mu L</math>)
 
• Hemoglobin (Hgb) <math>< 9</math> g/dL (90 g/L)
 
• Platelets (PLT) <math>< 75 \times 10^9/L</math> (<math>75 \times 10^3/\mu L</math>)
 
• Total bilirubin <math>> 1.5</math> x upper limit of normal (ULN)
 
• AST and/or ALT <math>> 3</math> x ULN, except for participants with liver metastasis who may not be included if AST and/or ALT <math>> 5</math> x ULN
 
• Alkaline phosphatase (ALP) <math>> 5</math> x ULN
 
• Calculated creatinine clearance <math>< 45</math> mL/min using Cockcroft-Gault formula
 
• Asymptomatic serum amylase or lipase <math>> \text{Grade } 2</math>
 
 
 

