--	--

	
 
• Serum amylase or serum lipase CTCAE grade <math>\geq 1</math> with signs and/or symptoms suggesting pancreatitis or pancreatic injury (e.g. elevated P-amylase, abnormal imaging findings of pancreas, etc.)
 
 
Participants in Phase II Group 5 have out of range laboratory values defined as:
 
 
• Absolute Neutrophil Count (ANC) <math><1.5 \times 10^9/L</math> (<math>1.5 \times 10^3/\mu L</math>) without growth factor support
 
• Hemoglobin (Hgb) <math><9</math> g/dL (90 g/L)
 
• Platelets (PLT) <math><100 \times 10^9/L</math> (<math>100 \times 10^3/\mu L</math>)
 
• Total bilirubin <math>>1.5</math> x upper limit of normal (ULN)
 
• AST and/or ALT <math>> 2.5</math> x ULN except for participants with liver metastasis, who may not be included if AST and/or ALT <math>> 5</math> x ULN
 
• Alkaline phosphatase (ALP) <math>>5</math> xULN
 
• Calculated creatinine clearance (using Cockcroft-Gault formula) <math>< 50</math> mL/min
 
• Asymptomatic serum amylase increase grade 1 and 2 are allowed if at the beginning of the study is confirmed to have no signs and/or symptoms suggesting pancreatitis or pancreatic injury (e.g., elevated P-amylase, abnormal imaging findings of pancreas, etc.)
 
• Serum lipase <math>> ULN</math>
 
 
 
• Participants who have impairment of GI function or GI disease that may significantly alter the absorption of study treatment (e.g., ulcerative diseases, uncontrolled nausea, vomiting, diarrhea, or malabsorption syndrome)
 
• For Phase II Group 5: Carcinomatous meningitis
 
• For Phase II Group 5: Known EGFR T790M positive, Known C797S positive, known druggable molecular alterations (such as ROS1, BRAF, KRAS etc.) who might be candidates for alternative targeted therapies as applicable per local regulations and treatment guidelines
 
• Participants who received live vaccines (e.g., intranasal influenza, measles, mumps, rubella, oral polio, Bacille Calmette-Guerin (BCG), yellow fever, varicella, TY21a typhoid vaccines and COVID 19 vaccines) within 30 days prior to the first dose of study treatment
 
 
Please refer to Section 5.3 for complete list of exclusion criteria

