### 5.3 Exclusion criteria

Participants eligible for this study must not meet **any** of the following criteria:

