4. Participants with symptomatic brain metastases. However, participants with asymptomatic/controlled brain metastases may participate in the trial. If treatment is required, these participants must have completed any planned radiation therapy and/or surgery > 2 weeks prior to the first dose of study treatment and remain asymptomatic. Participants must be neurologically stable, having no new neurologic deficits on clinical examination, and no new findings on central nervous system imaging. Participants taking steroids must have been on a stable dose for two weeks prior to the first dose of study treatment.

For Group 5: Participants with symptomatic CNS metastases who are neurologically unstable or have required increasing doses of steroids within the 2 weeks prior to study entry to manage CNS symptoms. If participants are on corticosteroids for endocrine deficiencies or tumor-associated symptoms other than CNS related, dose must have been stabilized (or decreasing) for at least 5 days before Cycle 1 Day 1.

5. Any medical condition that would, in the investigator's judgment, prevent the participant's participation in the clinical study due to safety concerns or compliance with clinical study procedures (e.g., active infection, inflammation, intestinal obstruction, unable to swallow medication, social/psychological issues, etc.). Any severe, acute, or chronic medical or psychiatric condition or laboratory abnormality or substance abuse that may increase the risk associated with study participation or study treatment administration or that may interfere with the interpretation of study results and, in the judgment of the investigator, would make the participant inappropriate for the study.

6. Presence or history of another malignancy.

Exception: Participants who have been disease-free for 3 years, or participants with a history of adequately treated in-situ carcinoma of the uterine cervix, completely resected basal or squamous cell carcinoma, non-melanomatous cancer of skin, history of stage IA melanoma that has been cured, are eligible.

For Group 5: Presence or history of a malignant disease other than NSCLC that has been diagnosed and/or required therapy within the past 3 years. Exceptions to this exclusion include completely resected basal cell and squamous cell skin cancers, and completely resected carcinoma in situ of any type.

7. Undergone a bone marrow or solid organ transplant.

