16. Participants (except those in Phase II Group 5) have not recovered from all toxicities related to prior anticancer therapies to grade  $\leq 1$  (CTCAE v 4.03). Participants in Phase II Group 5 will use version 5.0. Participants with any grade of alopecia are allowed to enter the study.
17. **Participants in Phase Ib and Phase II Groups 1 to 4** have out of range laboratory values defined as:
  - Absolute Neutrophil Count (ANC)  $< 1.5 \times 10^9/L$  ( $1.5 \times 10^3/\mu L$ )
  - Hemoglobin (Hgb)  $< 9$  g/dL (90 g/L)
  - Platelets (PLT)  $< 75 \times 10^9/L$  ( $75 \times 10^3/\mu L$ )
  - Total bilirubin  $> 1.5$  x upper limit of normal (ULN)
  - AST and/or ALT  $> 3$  x ULN, except for participants with liver metastasis who may not be included if AST and/or ALT  $> 5$  x ULN
  - Alkaline phosphatase (ALP)  $> 5$  xULN
  - Calculated creatinine clearance  $< 45$  mL/min (0.75 mL/sec) using Cockcroft-Gault formula
  - Asymptomatic serum amylase or lipase  $>$  Grade 2
  - Serum amylase or serum lipase CTCAE grade  $\geq 1$  with signs and/or symptoms suggesting pancreatitis or pancreatic injury (e.g. elevated P-amylase, abnormal imaging findings of pancreas, etc.)

Participants in Phase II Group 5 have out of range laboratory values defined as:

- Absolute Neutrophil Count (ANC)  $< 1.5 \times 10^9/L$  ( $1.5 \times 10^3/\mu L$ ) without growth factor support
- Hemoglobin (Hgb)  $< 9$  g/dL (90 g/L)
- Platelets (PLT)  $< 100 \times 10^9/L$  ( $100 \times 10^3/\mu L$ )
- Total bilirubin  $> 1.5$  x upper limit of normal (ULN)
- AST and/or ALT  $> 2.5$  x ULN except for participants with liver metastasis, who may not be included if AST and/or ALT  $> 5$  x ULN
- Alkaline phosphatase (ALP)  $> 5$  xULN

- Calculated creatinine clearance (using Cockcroft-Gault formula) < 50 mL/min
  - Asymptomatic serum amylase increase grade 1 and 2 are allowed if at the beginning of the study is confirmed to have no signs and/or symptoms suggesting pancreatitis or pancreatic injury (e.g., elevated P-amylase, abnormal imaging findings of pancreas, etc.)
  - Serum lipase > ULN
18. Participants have the following laboratory values outside of the laboratory normal limits or cannot be corrected to within normal limits with supplements during screening:
- Potassium
  - Magnesium
  - Phosphorus
  - Total calcium (corrected for serum albumin)
19. Participants receiving treatment with medications that are known to be:
- strong inhibitors or inducers of CYP3A4/5,

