g Note: If total bilirubin > 3.0 × ULN is due to the indirect (non-conjugated) component only, and hemolysis as the etiology has been ruled out as per institutional guidelines (e.g., review of peripheral blood smear and haptoglobin determination), then ↓ 1 dose level and continue treatment at the discretion of the investigator. h A CT scan or other imaging study to assess the pancreas, liver, and gallbladder must be performed within 1 week of the first occurrence of any ≥ grade 3 of amylase and/or lipase. If asymptomatic grade 2 elevations of lipase and/or amylase occur again at the reduced dose, participants will be discontinued permanently from study treatment. i Antidiarrheal medication is recommended at the first sign of abdominal cramping, loose stools or overt diarrhea. j During the whole duration of treatment with capmatinib, the participant is recommended to use precautionary measures against ultraviolet exposure (e.g., use of sunscreen, protective clothing and avoid sunbathing or using a solarium intensively).	

**Table 6-8 Dose modifications for capmatinib monotherapy (or if nazartinib permanently discontinued and capmatinib continued as monotherapy)**

Worst toxicity CTCAE Grade a during a cycle of therapy	Recommendation
No toxicity	Maintain dose level
HEMATOLOGICAL	
Neutrophil count decreased (ANC) Neutropenia	
Grade 1 (ANC < LLN - 1500/mm  ; < LLN - 1.5 x 10  /L)	Maintain dose level
Grade 2 (ANC < 1500 - 1000/mm  ; < 1.5 - 1.0 x 10  /L)	Maintain dose level
Grade 3 (ANC < 1000 - 500/mm  ; < 1.0 - 0.5 x 10  /L)	Omit dose until resolved to ≤ grade 2, then: 
 
• If fully resolved in ≤ 7 days, resume treatment at the same dose level
 
• If fully resolved in > 7 days, then resume at ↓ 1 dose level
 

Grade 4 (ANC < 500/mm  ; < 0.5 x 10  /L)	Omit dose until resolved to ≤ grade 2 and then resume at ↓ 1 dose level
Platelet count decreased (Thrombocytopenia)	
Grade 1 (PLT < LLN - 75,000/mm  ; < LLN - 75 x 10  /L)	Maintain dose level
Grade 2 (PLT < 75,000 - 50,000/mm  ; < 75 - 50 x 10  /L)	Maintain dose level

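### Read literally, the Group 5 neutrophil exclusion releases a participant whose count is below the limit while on growth factor; the Groups 1 to 4 bullet with the same limit excludes that participant

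*Protocol*

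**What the plan says.** Section 5.3 sets the direction of the list: "Participants eligible for this study must not meet" any of the criteria in it. Criterion 17 then gives two sets of laboratory limits. For Group 5 it opens with "Participants in Phase II Group 5 have out of range laboratory values defined as", and its first bullet is an ANC below 1.5 x 10^9/L followed by "without growth factor support". The protocol summary carries the same bullet with the same qualifier, so this is not a slip confined to one place.

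For Phase Ib and Phase II Groups 1 to 4, the parallel list (participants who "have out of range laboratory values defined as") has the same ANC limit and no mention of growth factor.

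Two other exclusions bear on the point. Criterion 16 removes participants who "have not recovered from all toxicities related to prior anticancer therapies to grade" 1 or below, with CTCAE version 5.0 used for Group 5. Criterion 5 lets the investigator exclude for, among other things, a "laboratory abnormality or substance abuse that may increase the risk associated with study participation".

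**The concern.** The qualifier belongs naturally in an inclusion criterion, where it demands a count at or above the limit that is reached unaided. Attached to an excluding value it works the other way: the criterion is met only if the count is low and no growth factor is being given. A phrase evidently meant to stop support from masking neutropenia then makes support a reason not to exclude.

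The surrounding text suggests that this was not intended. Several Group 5 limits that differ from those for Groups 1 to 4 are tighter: platelets 100 against 75 x 10^9/L, AST/ALT 2.5 against 3 x ULN without liver metastasis, creatinine clearance 50 against 45 mL/min, and lipase above ULN against above Grade 2. A looser neutrophil rule runs against that pattern. In criterion 10 the protocol handles a treated value the opposite way, counting raised blood pressure as excluding whether or not it is being treated.

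At stake is uniform application of an eligibility rule across sites, and the baseline against which Group 5 hematology changes and adverse events are read. Both are part of the secondary safety objective in Table 3-1.

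**Working it through.** No stated statistical figure is involved, so the check is a comparison of wordings.

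Inputs: the Group 5 ANC bullet (summary; Section 5.3, criterion 17), the Groups 1 to 4 ANC bullet (same places), criteria 5 and 16 (Section 5.3), and the neutropenia grading in Table 6-8.

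Step 1. Rules.
- Groups 1 to 4: excluded if ANC < 1.5 x 10^9/L.
- Group 5, literal: excluded if ANC < 1.5 x 10^9/L AND no growth factor support.

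Step 2. The four combinations.

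| ANC against the limit | Growth factor | Groups 1 to 4 bullet | Group 5 bullet, literal |
|---|---|---|---|
| below | no | excluded | excluded |
| below | yes | excluded | **not excluded** |
| at or above | yes | not excluded | not excluded |
| at or above | no | not excluded | not excluded |

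The two bullets differ in one row only: the low count under support.

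Step 3. What other criteria do with that row. Table 6-8 starts Grade 2 neutropenia below 1500/mm3 ("Grade 2 (ANC < 1500 - 1000/mm"), and 1500/mm3 equals 1.5 x 10^9/L. Every count in the row is therefore Grade 2 or worse.
- If the low count is an unrecovered toxicity of prior anticancer therapy, criterion 16 excludes the participant, on growth factor or not.
- If it has another cause, no fixed rule excludes. Criterion 5 may, but only by judgement.

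Step 4. Size. The residual group is: ANC below 1.5 x 10^9/L, on growth factor, not attributed to prior anticancer therapy, and not excluded by the investigator. The protocol gives no figure from which to estimate it. With about 30 participants planned for Group 5 (Section 4.1), each such participant is 1/30 = 3.3 percentage points of a Group 5 incidence rate. That is the weight of any single participant, not an estimate of distortion.

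**The case against.** The strongest reply is that the phrase can be read as describing the measurement: the count, taken without support, is below 1.5 x 10^9/L. On that reading a participant who reaches the limit only through growth factor is excluded. So is one who is low despite it, provided that support does not lower the count. This reading is possible, but the protocol gives no growth-factor-free interval or other means of establishing an unsupported count. Sites could reasonably apply either reading, and that is itself a reason to reword.

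The second reply is that criterion 16 already removes the most obvious cases and criterion 5 allows exclusion of others. This stands, and it is why the gap is small. Group 5 also enters after one prior line of EGFR TKI, with washout periods for earlier agents, so few participants are likely to be on growth factor at entry.

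Two stronger inferences are tempting, and the protocol does not support them. A reader might infer that a participant with ANC below 1.0 x 10^9/L on growth factor would start Cycle 1 already in the Table 6-8 Grade 3 row ("Omit dose until resolved to ≤ grade 2, then"), so that dose interruptions and dose intensity would be distorted from the first day. But Section 6.3.1 addresses drug-related toxicity, and Table 6-8 is keyed to the worst toxicity during a cycle of therapy; a count that predates the first dose is not shown to fall there. A reader might also infer that Group 5 is laxer for counts at or above the limit reached under support. The Groups 1 to 4 bullet does not exclude those either, so there is no difference between the groups on that row.

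**Conclusion.** The point holds as a wording defect in an operative eligibility rule. In Group 5 the qualifier, read literally, releases a participant whose count is below the limit while on growth factor, and the parallel bullet for the other groups does not. Criteria 16 and 5 leave only a small residual gap. It concerns eligibility and baseline safety; the definition of ORR, the predictive-probability futility rule and the planned sample size are unaffected. For counts at or above the limit reached under support, the text is ambiguous rather than wrong.

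The conclusion assumes that growth factors are not restricted elsewhere. The summary points to Section 5.3 for the complete exclusion list, and no other criterion there mentions them. The text I had stops at the start of Section 6.3.2, so the concomitant-medication sections and Table 7-2 are unchecked. A restriction on growth factor at entry there would narrow the gap further, though the bullet would still read the wrong way round.

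**What to change.** Keep the limit. Reword the Group 5 ANC bullet in both the protocol summary and Section 5.3, criterion 17, so that a count below the limit meets the exclusion whether or not growth factor is being given, consistent with the Groups 1 to 4 bullet.

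Separately, the sponsor should state what it intends for a count at or above the limit reached under growth factor support and bring the wording into line with that. If the intent is that the count must be reached unaided, the protocol also needs to say how an unsupported count is established. I propose no clinical rule on that.

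The rewording for low counts is one sentence in two places and needs no extra test or visit. Any cost attached to supported counts depends on the intent that the sponsor states.

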## 1 Background

### 1.1 Overview of disease pathogenesis, epidemiology and current treatment

Lung cancer is the most common cancer type worldwide, with an estimated 2.1 million new cases in 2018, representing 11.6% of all new cancers. It is also the most common cause of death from cancer, with 1.8 million deaths representing 18.4% of the total deaths from cancer (Bray et al 2018). In 2019, approximately 142,670 deaths due to lung cancer were expected in the United States (US) (Siegel et al 2019) and 280,000 in the European Union (Malvezzi et al 2019).

In Western countries, 10-15% non-small cell lung cancer (NSCLC) participants express epidermal growth factor receptor (EGFR) mutations in their tumors (accounting for 20000 to 30000 new participants per year in the USA), and Asian countries have reported rates as high as 30-40%. The predominant oncogenic EGFR mutations (L858R and exon 19 deletion (ex19del)) account for about 90% of EGFR mutant NSCLC. This results in the activation of multiple pathways that promote survival, proliferation, angiogenesis and metastasis (Mendelsohn 2000; Hirsch 2003; Lynch 2004; Paez 2004; Pao 2004). De novo EGFRT790M mutations are rare (<1% of all lung cancers) when identified by standard sensitivity methods and occur concurrently with EGFR mutations L858R or ex19del (Yu et al 2014).

EGFR is an established critical therapeutic target for lung cancer. Numerous trials with first generation EGFR inhibitors (e.g., erlotinib and gefitinib) and more recently with the second generation (e.g., afatinib) have been conducted in the EGFR mutant NSCLC population. These trials have consistently demonstrated superior efficacy of EGFR tyrosine kinase inhibitors (TKIs) over chemotherapy (Table 1-1). EGFR TKIs' response rates in EGFR mutant NSCLC participants range from approximately 60 to 80% versus 20 to 30% for the chemotherapy control arms. Similarly, median progression free survival (PFS) is prolonged via EGFR TKI first line treatment on average by 50%; ranging from 8 to 11 months, as compared to 4 to 6 months for chemotherapy control arms.

**Table 1-1 Superiority of EGFR TKIs over chemotherapy in EGFRmut NSCLC**

Trial	Compound	RR (%)		Median PFS (mo)		Median OS (mo)	
		TKI	Chemo	TKI	Chemo	TKI	Chemo
IPASS (mut+) (Mok et al 2009)	Gefitinib	71.2	47.3	9.5	6.3	21.6	21.9
First-SIGNAL (mut+) (Han et al 2012)	Gefitinib	84.6	37.5	8.4	6.7	30.6	26.5
WJTOG (Mitsudomi et al 2010)	Gefitinib	62.1	32.2	9.2	6.3	30.9	NR
NEJ002 (Inoue et al 2009)	Gefitinib	73.7	30.7	10.8	5.4	27.7	26.6
OPTIMAL (Zhou et al 2011)	Erlotinib	83	36	13.7	4.6	22.6	28.8
EURTAC (Rosell et al 2012)	Erlotinib	58	15	9.7	5.2	19.3	19.5
Afatinib (LUX-Lung 3) (Keating 2014)	Afatinib	56	23	11.1	6.9	28.1	28.2

Trial	Compound	RR (%)		Median PFS (mo)		Median OS (mo)	
		TKI	Chemo	TKI	Chemo	TKI	Chemo
Afatinib (LUX-Lung 6) (Keating 2014)	Afatinib	66.9	23	11	5.6	22.1	22.2

Although remarkable response rates are seen in participants with EGFR mutations that are treated with EGFR TKIs (~ 80%), the responses are of limited duration because eventually participants develop “acquired resistance”.

Several resistance mechanisms have been identified, the most common being a secondary mutation at the threonine gatekeeper residue at position 790, T790M, which develops in up to 50% of NSCLC participants harboring a primary EGFR mutation treated with first or second generation EGFR TKIs. Although the results from the [AURA3] and the [FLAURA] trials led to the approval of osimertinib (a third generation TKI with activity in NSCLCs harbouring the T790M mutation as first- and second-line treatment), it should be noted that 20% of these participants did not respond to osimertinib. C797S mutation was observed in one third of this resistant population, the osimertinib resistance could be linked to the novel C797S mutation, whereas in many other cases MET amplifications as a resistance bypass mechanism causing EGFRmut-TKI resistance have been identified suggesting that a combination of a MET and a EGFRmut inhibitor may be of benefit to overcome the observed resistance in these NSCLC participants (Papadimitrakopoulou et al 2018, Ramalingam et al 2018). The basic mechanism by which MET amplification causes EGFR-TKI resistance is associated with the activation of EGFR-independent phosphorylation of ErbB3 and downstream activation of the PI3K/AKT pathway, providing a bypass signaling pathway even in the presence of an EGFR-TKI (Engelman et al 2007) suggesting that co-targeting both, EGFR and MET is required to overcome resistance to EGFR-TKIs due to MET amplification. The MET amplification in NSCLCs was found to be 2–5%. However, the incidence of MET amplification was higher in NSCLC participants treated with erlotinib or gefitinib, ranging from 5% to 22% (Liang and Wang 2020). Several lines of evidence, however, suggest that MET gene amplification is another important mechanism for TKI resistance in NSCLCs and is detectable in approximately 5–22% of NSCLC participants with acquired resistance to first-generation EGFR-TKIs (Wang et al 2018).

The following results were reported from a phase Ib/II study with capmatinib and gefitinib in NSCLC participants with acquired resistance to gefitinib, erlotinib, or afatinib and MET amplifications (gene copy number  $\geq 6$ ) (Wu et al 2018). Overall, 61 participants were treated in phase Ib and 100 participants were treated in Phase II. In the phase Ib part ORR was 23% across all doses and was regardless of the MET status. Increased activity, however, was observed in participants with a high MET copy number, with a Phase II ORR of 47%. The most common drug-related adverse events were nausea (28%), peripheral edema (22%), decreased appetite (21%), and rash (20%). In contrast to a number of other combination studies, the combination of capmatinib and gefitinib was found to be tolerable. From this study the authors concluded that capmatinib in combination with an EGFRmut TKI can restore sensitivity in TKI-resistant NSCLC participants harbouring EGFR mutations. The contribution of a capmatinib alone, however, was not evaluated.

Collectively, MET amplification is observed as one of the key resistant mechanism of EGFR TKIs.

Combination treatment of MET inhibitor and EGFR TKI showed a clinical meaningful response rate in high MET copy number participants who progress on EGFR TKI treatment. However, there is very limited data regarding efficacy of MET inhibitor monotherapy in the EGFR TKI resistant population to demonstrate the contribution of component in the combination therapy.

[figure not shown]
